The number of individuals living with PD in the most populous nations is expected to increase to approximately 9 million by 2030.¹⁸ Developing strategies to support older individuals who are faced with a chronic health condition as well as cultural and structural barriers to physical activity and exercise must be prioritized to maximize best outcomes for quality of life. A peer-supported physical activity intervention using a culturally and linguistically tailored program could increase physical activity and improve disease self-management for Hispanic individuals living with PD. Engaging with a trusted peer who is also living with the same disease may provide access to health information as well as vicarious experiences, mastery experiences, and social persuasion to effect behavior change. Our approach offers a novel, scalable, and generalizable means to increase physical activity and enhance disease self-management. This work has the potential to impact under-served individuals world-wide living with PD and, potentially, millions more with other chronic progressive conditions.

Hypotheses or Research Question, Aims and Objectives:

- Hypothesis/Question: Is a peer partner training program and a peer-supported, mobile health, physical activity intervention feasible in Latinx people with PD?
 - Exploratory hypothesis: A peer partner training program and a peer-supported, mobile health, physical activity intervention will increase physical activity, motivation, quality of life and self-efficacy for physical activity in participants. This intervention will be most beneficial to those that are classified as sedentary (< 5,000 steps/day) at baseline.
- Aims / objectives
 - **Aim 1: To culturally adapt and determine feasibility of the peer partner training program.**
We will examine (1A) acceptability (1B) appropriateness (1C) feasibility and (1D) cultural

relevance through self-report surveys and qualitative interviews with study participants. (1E) We will examine knowledge acquisition with a pre and post knowledge quiz. (1F) We will examine training engagement with attendance at the 2 virtual training sessions.

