To support an increase in physical activity, participants will have access to a weekly virtual synchronous bilingual exercise class that is geared towards the needs of people with PD. The class will have 3 areas of focus: aerobic exercise, resistance exercise (using body weight), and balance, breathing, and stretching exercise. The first 3 weeks will focus on aerobic exercise, the second 3 weeks on resistance training and the last 2 weeks will focus on balance, breathing and stretching exercise. All exercise classes will be tailored to the needs of people with PD and designed by a physical therapist with a specialization in neurologic physical therapy (PI-[name]) and a fitness instructor with a certificate from the American Parkinson Disease Association for Fitness Professionals. The instructor will provide modifications of the exercises so that individuals can participate at the level that is suited to their status.

Outside of the exercise class, participants will be encouraged to increase their walking and general physical activity. For example, peer pairs may develop a goal to increase their steps by 1,000 steps/day and may develop a plan to march in place during commercials when watching their favorite television show.

Post-assessment

Baseline measures will be repeated at the conclusion of the intervention as presented above. They will include:

- a. **Physical Activity Scale for the Elderly**
- b. **Behavioral Regulation in Exercise Questionnaire-2**²¹⁻²³
- c. **Parkinson Disease Questionnaire-39 (PDQ-39)**²⁴
- d. **Self-Efficacy for Physical Activity (SEPA)**^{25,26}

e. GDS-15

f. LARS

Participants will receive a phone call to complete the aforementioned assessments.

In addition, the following surveys, **Acceptability of Intervention Measure (AIM)**, **Intervention Appropriateness measure (IAM)**, and **Feasibility of Intervention Measure (FIM)** will be completed via ReDCAP. (If individuals are unable to complete the survey online, they will receive a physical copy of these surveys through standard mail with a self-addressed envelope to return to the research team.) Each measure has 4 items that assess acceptability, appropriateness, and feasibility, respectively. They are constructed at a 5th grade reading level with a Likert scale that ranges from completely agree to completely disagree. Validity (α from 0.85-0.91) and reliability (0.73-0.88) were high for all three scales.²⁵ (approximately 15 minutes to complete all 3 surveys)

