Content and thematic analysis of qualitative data; descriptive statistics to characterize the sample and measure feasibility.

- Aim 1 analysis
 - Scores equal to or greater than 75% on the Acceptability of Intervention Measure (AIM), Intervention Appropriateness measure (IAM), and Feasibility of Intervention Measure (FIM) are set to determine acceptability, appropriateness, and feasibility of the peer partner training.
 - Cultural relevance of the peer partner training will be determined through content analysis of focus group discussions
- Aim 2 analysis
 - Peer engagement will be successful if connecting $\geq 80\%$ of the recommended times over the course of the intervention period.
 - Scores equal to or greater than 75% on the Acceptability of Intervention Measure (AIM), Intervention Appropriateness measure (IAM), and Feasibility of Intervention Measure (FIM) are set to determine acceptability, appropriateness and feasibility of the peer partner intervention.
- Exploratory aim analysis
 - Group means will be compared from baseline to post-intervention using paired t-tests to assess change in physical activity levels (Physical Activity Scale for the Elderly & objectively measured physical activity through the activity monitor), motivation (Behavioral Regulation in Exercise Questionnaire), quality of life (Parkinson Disease Questionnaire-39 (PDQ-39)), depression (GDS), apathy (LARS) and self-efficacy for physical activity (Self-Efficacy for Physical Activity (SEPA)).

Dissemination: The results of this research will be disseminated at a professional conference in a poster or platform presentation. After receiving feedback from this presentation, results will be disseminated in a peer-

reviewed scholarly journal. Additionally, if the results from this research are promising, it will be used to inform a randomized controlled trial of the intervention.

PROTECTION OF HUMAN SUBJECTS

Risks to Human Subjects:

Physical Risk

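### The 75% rule on AIM, IAM and FIM is set for both the training and the intervention, but only one set of these surveys is described and what it rates is not stated

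*Combined protocol and SAP*

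**What the plan says.** The aims treat the training and the 8-week programme as separate objects of assessment. For the training, Aim 1 reads "We will examine (1A) acceptability (1B) appropriateness (1C) feasibility and (1D) cultural" relevance, using self-report surveys and interviews; 1E is a knowledge quiz and 1F is attendance. Aim 2 lists acceptability, appropriateness and feasibility of the intervention as 2B to 2D, from the same kinds of source.

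METHOD(S) OF DATA ANALYSIS turns this into a numeric rule, stated twice. Under Aim 1, AIM, IAM and FIM scores of 75% or more "are set to determine acceptability, appropriateness, and feasibility of the peer partner training". Under Aim 2, the same scores and cut-off "are set to determine acceptability, appropriateness and feasibility of the peer partner intervention".

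The surveys themselves are described only under Post-assessment, after the intervention, by ReDCAP or on paper. "Each measure has 4 items that assess acceptability, appropriateness, and feasibility, respectively", and the time given is "approximately 15 minutes to complete all 3 surveys". The text names the construct behind each measure, but not whether the respondent is rating the training or the 8-week programme.

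**The concern.** A decision rule needs a score that refers to the thing being decided. Here two rules, about two different components, point to the same three measures, and the schedule describes one collection of them. If a score falls below 75%, the team would want to know whether to revise the videos and training meetings or the 8-week programme. Dissemination says that "if the results from this research are promising, it will be used to inform a randomized controlled trial of the intervention", so the answer bears on what is carried forward. Ratings that were never collected separately cannot be separated in the analysis.

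**Working it through.** No sample-size or error-rate calculation is involved. The check is to count criteria against described scores, and then to size the remedy.

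**Criteria against scores**
- Criteria: 3 for the training (1A, 1B, 1C) + 3 for the intervention (2B, 2C, 2D) = 6.
- Scores described per participant: AIM, IAM, FIM = 3, from 3 × 4 = 12 items.

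**Other places where a training rating could have been scheduled**
- Orientation Session: a knowledge quiz, plus instruction on filling in online surveys. No survey is named and no time point is given.
- Peer partner training: two review meetings, then a final meeting with check-off sheets and a quiz. The final meeting is the natural slot for rating the completed training, and it lists no AIM, IAM or FIM.
- Weekly research assistant calls: peer contact, barriers, technology needs and adverse events.
- Focus group: held after the 8 weeks. It covers acceptability, appropriateness and feasibility without separating training from programme, and mentions cultural relevance for the intervention only.

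The analysis section uses the focus groups for the training in one way: "Cultural relevance of the peer partner training will be determined through content analysis of focus group discussions". That serves 1D. It gives no rule by which focus-group material would decide 1A to 1C.

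**What follows under each reading**

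| Reading | Consequence |
|---|---|
| One set feeds both aims | 3 scores serve 6 criteria; the Aim 1 and Aim 2 survey verdicts are identical by construction |
| The set rates the intervention only | 3 scores serve 3 criteria; 1A to 1C have no survey score |
| Two versions are given | 6 scores serve 6 criteria; the second version is undocumented |

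The tracker is issued once training is complete and is worn for 8 weeks before post-assessment. A training rating collected at post-assessment therefore comes at least 8 weeks after training ended.

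**Burden of a second set, from the protocol's own times**
- Repeated measures listed under Post-assessment, in minutes: PASE 15 + BREQ-2 10 + PDQ-39 10 + SEPA 2–3 + GDS-15 5 + LARS 15–20 = 57–63.
- With the present AIM/IAM/FIM set: 57–63 + 15 = 72–78.
- With a second set: 72–78 + 15 = 87–93. Increase: 15/78 = 19% to 15/72 = 21%.
- If PHQ-8 (5) and the Sallis survey (10) are also repeated, the base is 87–93 and the total 102–108. Increase: 15/93 = 16% to 15/87 = 17%.
- Whole study: 20 × 15 = 300 minutes = 5 hours at most.

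**The case against.** The strongest reply is that two versions may well be intended. The two rules name different objects, which fits two versions at least as well as one shared set. The stated time is compatible with this: 15 minutes over 12 items is 75 seconds per item, while over 24 items it is 37.5 seconds. The protocol's other times run from about 15 seconds per item (PDQ-39: 600/39) to 37.5 seconds (PHQ-8: 300/8), and only PASE, at 90 seconds, is slower than 75. This stands as a possibility. It is not a description: the text speaks of three surveys and never of two versions.

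A reader might infer that the two verdicts must coincide. That holds only if one set feeds both aims, which the documents do not state.

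A reader might also infer that Aim 1 is left without data. It is not: 1D has the focus groups, 1E the quiz and 1F attendance, and the focus groups can give qualitative information on 1A to 1C. What 1A to 1C lack, on the schedule as described, is a survey score of their own to which the stated rule could be applied.

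It would be unfair to hold every training-phase meeting against the plan. Orientation comes before the videos and the first review comes midway, so neither could host a rating of the completed training.

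Finally, every participant receives both components, the research question joins them, and no stated action depends on the two aims passing separately. This limits the seriousness. It does not remove the mismatch between two separately stated rules and one described set.

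**Conclusion.** The point holds as a gap between the decision rules and the described data collection. Six criteria face three described scores, and the rated object is not named. Either the Aim 1 and Aim 2 survey verdicts on these constructs are the same by construction, or three of the six Aim 1 objectives (1A, 1B, 1C) have no survey score. The second matters because the 75% rule is the only numeric criterion that the analysis section sets for Aim 1.

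This is conditional on the schedule as written. If two versions already exist, the defect shrinks to an undocumented second set. Sample size and error rates are not affected. It should be fixed because separate ratings cannot be reconstructed later, but it does not undermine the study as a whole.

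**What to change.** 1. Under Post-assessment, state that two separately worded and labelled AIM/IAM/FIM sets are given, one about the peer partner training and one about the 8-week intervention.
2. In METHOD(S) OF DATA ANALYSIS, state that the Aim 1 rule uses only the training set and the Aim 2 rule only the intervention set.

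**If two versions already exist**, this is a wording change with no added participant time.

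**If they do not**, add the training set: 12 items and about 15 minutes per participant, within the total worked out above. Staff must word, translate and back-translate the changed text. Those who cannot respond online are covered by the existing arrangement: "they will receive a physical copy of these surveys through standard mail".

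**Timing.** Giving both sets at post-assessment is the minimum. Optionally, the training set can be self-completed in ReDCAP after the final training meeting. This avoids the delay of at least 8 weeks and captures people who leave after training; the risk section foresees that a peer may drop out. The price is that the training is rated before it has been used, so views after use would come only from the focus groups.

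**Downsides.** Questionnaire time rises by 19% to 21% if the Post-assessment list is exhaustive, or by 16% to 17% if PHQ-8 and the Sallis survey are also repeated. That time is spread over telephone and self-completed surveys rather than one sitting. Two similar sets given side by side may also be answered alike.

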- e. How can I help someone else living with Parkinson's disease?

There will then be a synchronous virtual meeting that is led by the research team to review the content of the first 6 videos. (approximately 30 - 45 minutes)

The additional 6 videos will cover the following topics related to peer and social support:

- f. Active listening
- g. Creating SMART goals for exercise

- h. Checking in: getting feedback on exercise goals
- i. Identifying facilitators for exercise
- j. Problem-solving and overcoming barriers to exercise
- k. Family and community support for exercise

There will then be a second synchronous virtual meeting, led by the research team, to review the content of the last 6 videos to ensure comprehension and baseline knowledge. (approximately 30 - 45 minutes)

There will be a final synchronous meeting to review check-off sheets that will guide weekly discussions and a knowledge check will be completed through a brief quiz. (approximately 30 - 45 minutes)

Peer-supported mobile health physical activity intervention (*Compañeros con Parkinson's*)

All participants will be peer partners (supporters). Individuals will be matched with a peer of the same gender. Attempts will be made to match those with additional similar traits, such as age, physical activity level, work status, and country of origin. Participants in each matched pair will support one another as they both strive to improve their physical activity.

After participants have completed the training, they will receive a commercially available activity tracker (Fitbit Inspire 2) and instructions on its use. They will wear this activity tracker for the duration of the 8-week period except for showering/bathing. Peers will download the FitBit application on their smart phone or tablet. Participants will be asked to log in to the FitBit app daily to sync their data with the app. If they do not have a smartphone or tablet, one will be provided to them, along with a data plan for the duration of the study. They can choose to have assistance with downloading the app from a research assistant. They can receive basic training on its use with the support of a research assistant via a telephone call or virtual meeting.

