Peers will become “FitBit Friends/*Amigos*” through the FitBit application. Peer pairs will be able to see each other’s accumulated steps over the week and communicate as a pair. This will connect 2 participants into a peer pair. Peer pairs can provide social support to each other through the app with comments and emojis. Participants will be asked to open the FitBit app daily to sync their data with the app. Additionally, peer pairs will establish a weekly meeting schedule by telephone or virtual meeting platform. Weekly meetings will be guided by check-off sheets to ensure critical content is covered and discussion of goal status is completed. Participants will be encouraged to participate in a weekly bilingual virtual exercise class that is synchronous.

In addition, all participants will join a FitBit closed group of *all* participants in the study. This group will be created by the research team and is not publicly available to others. It will be moderated by a research assistant and daily informational and motivational content will be posted. Participants can provide social support to each other in the group through the app with comments and emojis.

Weekly Meeting Calls Topics of Discussion (approx. 15- 30-minute discussions, 1x/week for 8 weeks)

1. Getting acquainted and building rapport; identifying core values; becoming “FitBit friends/*amigos*”
2. Establishing SMART goal (short-term/weekly and overall/8 week) and tying in with core values
3. Action Plan (Goal Check)
4. Benefits of Exercise (Goal check)
5. Feedback on Goals (Goal Check)
6. Facilitators/Barriers of Exercise (Goal check)
7. Family Support for Exercise/ Local and National Exercise Resources (Goal check)
8. Re-establishing goals/Sustaining exercise/Wrap up (Goal check)

A research assistant will call participants each week to determine if the weekly peer interaction call has been completed, to assist with any barriers to peer connection, and to assess technology needs. The research assistant will also assess for adverse events during this call. The RA will be guided by the adverse events form.

Support for an increase in physical activity

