Participants will be asked to again wear the **Actigraph GTX9** for 10 days post-intervention, following the procedures noted for baseline assessment.

Focus group

After the 8-week intervention period is completed, participants will participate in one of 2 focus groups (10 participants per group) with a semi-structured interview format to further discuss acceptability, appropriateness, and feasibility. In addition, participants will discuss the cultural relevance of the intervention. The focus group will be held on a virtual meeting platform. Participants will have the choice to participate with their camera on or off. The discussion will be moderated by a research assistant. (Approximately 60 minutes)

A device/tablet/data plan for 3 months will be provided to participants, if they do not have one, so that they can participate in the study. We will ask participants to return the device/tablet at the conclusion of the study. We will provide them with a stamped and self-addressed envelope for the return of the device.

Length of subject's participation in the study including number of visits, frequency of visits, and length of visits: Participant's participation in the study will be via remote interactions. The number, frequency and length of sessions are noted above.

CONSENT PROCESS:

The informed consent process will occur either electronically or by standard mail combined with phone calls with the study team. Consent will be initiated, questions answered, and the informed consent form signed before any other study procedures are performed. The informed consent form will be signed electronically through a ReDCAP forms or via standard mail (with a provided self-addressed/stamped return envelope).

Consent Procedure: (Approximate time = 30 minutes) Potential participants who express interest in participating in the study and clear pre-screening questions will be provided with the option to provide informed consent electronically or to receive a hard copy of the consent to sign once received via standard mail. If electronic consent is selected, the participant will choose a time to speak with an authorized consenter to review and submit the form together while on the telephone.

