The FitBit data will be housed on the FitBit device and might be subject to a loss of confidentiality. Only those that have the email and password for the FitBit account will have access to this data. This data will be downloaded to an encrypted and password protected UConn computer during the course of the study. Once the study is over the password will be changed so that only the individual has access to their FitBit data.

Participants will be matched with another person with PD and communicate with this person once per week during a virtual meeting. Participants will be FitBit friends and see each other's steps per week. There is a risk of conflicts between the peer partners. One person in the peer pair may drop out of the study. We will attempt to create a successful match by matching peers with others with similar characteristics (age, retired

vs working, stage of the disease, etc.). If there is a conflict between peer partners, a research assistant will be available to meet with the pairs to help resolve the conflict. If a peer partner drops out, we will attempt to reassign the participant to another partner.

Other risks

Survey administration may make participants feel uncomfortable answering some of the questions. Participants will be instructed that they can choose not to answer any questions that make them feel uncomfortable.

References:

3. Alberts JL, Rosenfeldt AB. The Universal Prescription for Parkinson's Disease: Exercise. *J Parkinsons Dis*. 10(Suppl 1):S21-S27. doi:10.3233/JPD-202100

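### The plan makes no provision for leavers' AIM/IAM/FIM ratings, and its 80% peer-contact rule does not say whether leavers stay in the count

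*Combined protocol and SAP*

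**What the plan says.** In the combined protocol and SAP, the Aim 2 analysis (Method(s) of Data Analysis) sets two kinds of criterion. Scores on AIM, IAM and FIM must reach 75%. Peer engagement succeeds at 80% or more "of the recommended times over the course of the intervention period". Neither criterion names the set of people counted or the unit.

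The number of recommended contacts comes from Weekly Meeting Calls Topics of Discussion: "1x/week for 8 weeks", so 8 meetings. These are tracked as they happen: "A research assistant will call participants each week to determine if the weekly peer interaction call has been completed".

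AIM, IAM and FIM appear only under Post-assessment, through ReDCAP; for people who cannot complete them online, "they will receive a physical copy of these surveys through standard mail". The Focus group section reads "After the 8-week intervention period is completed, participants will participate in one of 2 focus groups (10 participants per group"), which is 2 x 10 = 20, the full enrolment target.

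Loss is foreseen in the peer-matching text under Risks to Human Subjects: "One person in the peer pair may drop out of the study". The response is operational: the team will try to find the remaining person a new partner. On initial pairing, the intervention section says "Individuals will be matched with a peer of the same gender" and "This will connect 2 participants into a peer pair".

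**The concern.** Feasibility is the trial's main question, and promising results are to inform a randomized trial. Two separate gaps bear on that verdict.

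The first concerns what is collected. If people who leave rate the programme lower than those who stay (plausible, but not stated in the documents), scores gathered only at the end describe the stayers and look better than they would for everyone who started. An answer that was never requested cannot be recovered later.

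The second concerns what is counted. The weekly checks give call data up to the time of leaving, so the contact rate can be computed in several ways. Without a stated denominator, the choice could be made after the data are seen. The pair structure adds to this: one departure can remove calls from two people, and the plan does not say how weeks without a partner count.

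**Working it through.** **Inputs from the documents:** 20 participants; pairs of two; 8 weekly meetings; pass marks of 80% (contacts) and 75% (surveys). The sample size is justified only by comparability with other feasibility trials, so there is no power or attrition figure to reproduce.

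**Assumptions:** number of leavers, calls made before leaving, completers' call rate and all survey scores. None of these is in the documents.

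**Contact rule, pooled.** If all 20 are paired, expected participant-calls are 20 x 8 = 160 (80 pair meetings). The pass mark is 0.80 x 160 = 128 (64 meetings). A person at 85%, 90% or 95% makes 6.8, 7.2 or 7.6 calls.

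Rate over all paired = (calls by those who stay + calls by leavers and stranded partners) / 160.

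| Assumed case | Calculation | All paired | Completers |
|---|---|---|---|
| 4 leave after 2 calls, partners re-paired, completers 90% | (16 x 7.2 + 4 x 2)/160 | 77%, fail | 90%, pass |
| Same, leavers made 4 calls | (16 x 7.2 + 4 x 4)/160 | 82%, pass | 90%, pass |
| Same as first, completers 95% | (16 x 7.6 + 4 x 2)/160 | 81%, pass | 95%, pass |
| Same as first, completers 85% | (16 x 6.8 + 4 x 2)/160 | 73%, fail | 85%, pass |
| 2 leave after 0 calls, partners re-paired, completers 90% | 18 x 7.2/160 | 81%, pass | 90%, pass |
| 2 leave after 2 calls, partners not re-paired and also stop at 2, others 90% | (16 x 7.2 + 4 x 2)/160 | 77%, fail | 90% in intact pairs, pass |
| Same, others 95% | (16 x 7.6 + 4 x 2)/160 | 81%, pass | 95% in intact pairs, pass |
| 1 leaves, partner not re-paired, both at 0 calls, others 90% | 18 x 7.2/160 | 81%, pass | 90% in intact pairs, pass |

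In the first case the tipping point is (128 - 16 x 7.2)/4 = 3.2 calls: below that average among the 4 leavers, the all-paired rate fails. The pair-level count agrees when two whole pairs leave: (8 x 7.2 + 2 x 2)/80 = 77%.

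Per participant, 80% of 8 is 6.4, so a person needs 7 of 8 calls. The plan does not say how many participants would have to reach that.

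**Survey rule read as a group mean.** The mean over all 20 falls below 75% when the leavers' mean is below (20 x 75 - completers x their mean)/leavers.

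- Completers at 80%, 4 leavers: (1500 - 16 x 80)/4 = 55%.
- Completers at 80%, 2 leavers: (1500 - 18 x 80)/2 = 30%.
- Completers at 85%, 4 leavers: (1500 - 16 x 85)/4 = 35%.

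**Survey rule read as a share of participants.** With 4 lost, 12 of 16 favourable is 75% and passes. Over all enrolled it is 12/20 = 60% if none of the leavers would be favourable. Reaching 15 of 20 would need 3 of the 4 leavers to be favourable.

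**The case against.** The strongest reply is that the plan is silent rather than restrictive. Post-assessment and Focus group speak of participants, not completers; the surveys are remote, and the focus groups are sized for all 20. A reader might infer that the Aim 2 verdicts would rest mainly on completers. The documents do not support that for the contact rule: the wording, with 8 scheduled meetings, can equally be read as a fixed 8 for everyone paired, a reading with no survivor bias. The defect there is an undefined denominator, and the weekly checks make it correctable at analysis.

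A reader might also infer that partners of two leavers of different genders cannot be re-paired with each other. Same-gender matching is stated for initial pairing only; the reassignment sentence carries no gender condition. The inference holds only if the matching rule extends to reassignment. The not-re-paired cases above also assume no group of three and no new enrollee as partner; the documents describe neither.

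The survey tipping points need leavers to score far below completers, and no dropout rate is given. The consent form is not in the visible text, so the terms for contact after withdrawal cannot be checked.

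What stands is that foreseen dropout meets a survey scheduled only at the end, with no described route to leavers' ratings, and that the 80% rule leaves open a choice that can decide the result.

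**Conclusion.** The concern holds in two distinct parts, as something the sponsor should change.

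The AIM, IAM and FIM verdicts for Aim 2 are exposed to survivor bias that analysis cannot repair. Whether bias occurs, and how much, depends on how many leave and how they would have answered. With no dropout there is none. Under the mean reading a reversal needs a large gap between leavers and completers; under the share reading it needs less.

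The 80% rule admits at least two readings, and they disagree in some plausible cases and agree in others. Four leavers after 2 calls with completers at 90% reverse the verdict. The same leavers with completers at 95% do not, and neither does a single leaver with completers at 90%.

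Confidence is medium: the gaps are plain in the text, but every size rests on assumed dropout, call rates and scores.

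**What to change.** 1. Offer the existing ReDCAP or mailed AIM, IAM and FIM at withdrawal to anyone who leaves after pairing, where consent allows the contact. Report scores with and without leavers' responses, beside the number of non-responders. State whether 75% is a group mean or a share of participants.

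2. Define the 80% rule as completed calls over all paired participants x 8 scheduled meetings (160 participant-calls if all 20 are paired, pass mark 128). Count meetings not held after a withdrawal as missed, credit calls with a new partner, and show separately the meetings missed for lack of a partner. Give the completer figure as secondary.

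A tipping-point analysis of the survey scores and a threshold for class attendance are optional.

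The cost is a few sentences of wording and one survey contact per leaver, which the protocol puts at about 15 minutes for all three measures. Call completion is already checked weekly. Some leavers will decline, and the figures may be slightly less favourable.
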